# 15.1.6. Subject Activities Between Successive Study Visits (Visit 2 Through Visit 11), and Activities of Study Contacts 4, 6, 8, and 10 - Segment 1 - RP Cohort

Subjects will use moroctocog alfa (AF-CC) for hemophilia A treatment (protocol-defined prophylaxis [including treatment of any bleed, if necessary, during prophylaxis]). Subjects will document all of their infusions (dose, time of infusion, and reason) and all bleeding episodes in the Subject Diary. In addition, subjects will record the efficacy of a study drug infusion given on-demand for treatment of a bleed using a 4-point ordinal scale of "Excellent," "Good," "Moderate," and "No Response" in the Subject Diary (please refer to Section 18.1.3 for description of scale). Subjects will also document any AEs or use of concomitant medications in the Subject Diary. Subjects will save used study drug vials; used study drug vials are returned at each study visit. Approximately 4 weeks (±1 week) after study visit 3, and approximately 6 weeks ( $\pm 1$  week) after study visits 5, 7, and 9, respectively, the investigator (or designee) will contact the subject by telephone in order to collect information regarding the occurrence of any AEs, the use of concomitant medications, and study compliance. During these contacts, the investigator (or designee) will also review the subject's hemophilia A treatment (ie, investigator-prescribed on-demand therapy, or protocol-defined prophylaxis). The investigator (or designee) will also review information related to regimen escalation (criteria for, and subsequent action; see Section 15.3.3) with the

subject and will ensure that the criteria for regimen escalation had not been met. In addition, any change in a subject's prophylaxis regimen must be recorded; changes in the prophylaxis regimen should only occur in the event that escalation criteria are met. These study contacts, following study visits 3, 5, 7, and 9 are referred to as study contacts 4, 6, 8, and 10, respectively. (*Note*: Study contact information may be collected at an appropriately scheduled clinic visit, if the subject or the investigator prefers).

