- 6. For the exploratory analysis in RP cohort subjects, to test for the presence of treatment sequence, period and carryover effects, SAP Section 3.3.2.2 states that the ANOVA model will be fitted with terms for treatment sequence (AB or BA), treatment frequency (A or B), period (study segment 1 or 2), carryover and subject nested in treatment sequence. However, this model is overparameterized. Instead, the more appropriate mixed-effect model ABR=sequence period treatment, with subject as a random effect will be used to evaluate the treatment effect. Contrasts will be constructed to test if the carryover effect for each sequence is the same, and if the same, if that carryover effect is equal to zero.
- 7. Protocol Amendment 10 has text in section 15.2 (also appears in SAP Section 2.2) which states that the pharmacokinetic dose will be prepared from a single lot. However, multiple lots were used over the course of this study.
- 8. Protocol Amendment 10 has text in sections 22 and 22.6 (also appears in SAP Section 3) which indicates that both efficacy and safety will be reported separately for the 2 cohorts (OD and RP). However, only efficacy data is presented separately, and safety data is presented for all subjects combined.

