1.3. Design

This 2-segment study will be conducted as a multicenter, open-label, stratified, randomized evaluation of moroctocog alfa (AF-CC) in approximately 72 pediatric subjects (<16 years of age) with moderately severe to severe hemophilia A.

For segment 1, all subjects will use moroctocog alfa (AF-CC) in 1 of 2 treatment settings: on-demand (OD) therapy for 6 months (OD cohort) or prophylaxis for a 12-month period (RP cohort). Subjects who practice prophylaxis will be randomized to one of two regimens. The two prophylaxis treatment regimens, each delivering approximately 90 IU/kg/week, but differing in dosing schedule, will be:

A: 45 ± 5 IU/kg, administered twice a week

B: 25 ± 5 IU/kg, administered every other day

For segment 2, all subjects will use moroctocog alfa (AF-CC) for a 12-month period of prophylaxis treatment. Subjects who practiced on-demand therapy during segment 1 will practice prophylactic regimen B, defined above. Subjects who practiced prophylaxis during segment 1 will crossover to the other prophylactic treatment. A subset of subjects will participate in assessments for moroctocog alfa (AF-CC) PK characterization. This subset of subjects will undergo a baseline PK assessment, receiving a single open-label dose of moroctocog alfa (AF-CC) (50 \pm 5 IU/kg) with blood sampled for FVIII activity measurements before and at 0.5, 8, 24, 28 (optional), and 32 hours after the infusion.

Subjects on on-demand therapy for segment 1: Subjects who practice on-demand therapy at the time of the screening visit may continue to practice on-demand therapy with moroctocog alfa (AF-CC) in segment 1 (6-month period). These subjects will then practice prophylaxis regimen B for their 12-month period (segment 2) of treatment.

Subjects on prophylaxis treatment for segment 1: Subjects who are not assigned to the ondemand cohort in segment 1 will practice prophylaxis with moroctocog alfa (AF-CC) for both segments of the study and will be randomized in a 1:1 ratio to 1 of 2 treatment sequences (AB or BA) for a crossover evaluation of moroctocog alfa (AF-CC). Thus, subjects who practiced prophylaxis regimen A during segment 1 will crossover to prophylactic regimen B in segment 2 and vice versa. Randomization of these subjects will also be stratified by hemophilia A severity: FVIII activity <1% or 1-2% (central laboratory screening result).

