3.3.2.1. Variable Definition

To assess the efficacy of routine prophylaxis, the ABR will be derived for each subject for each prophylaxis regimen by using the following formula:

ABR = number of bleeds / (Days on treatment regimen/365.25)

The number of bleeds for the ABR calculation includes all bleeds requiring treatment with a FVIII replacement product during the time on treatment. For segment 1 prophylaxis, days on treatment regimen for this calculation is defined as (date of visit 11 – date of visit 2) +1. For segment 2 prophylaxis, days on treatment regimen for this calculation is defined as (date of visit 19 – date of visit 11). If a subject does not complete a study segment, the days on treatment ends at the last study visit. The ABR will be calculated 3 ways: 1) including all data from the ITT population (all RP subjects), 2) including all data from the PR_A-PR_B population and 3) including all data from the PR_A-PR_B population except the first month of each segment (considering the first month to be a washout period and allowing for an analysis of the sensitivity of ABRs to previous therapy).

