3.3.2.2. Analysis Method

The null hypothesis is that there is a difference in ABR between the two prophylaxis regimens. The alternative hypothesis is that the two prophylaxis regimens are similar enough to be considered clinically equivalent.

The 90% 2-sided confidence interval (CI) for the mean difference in ABRs for the 2 prophylaxis regimens for ITT subjects will be constructed using the t distribution with n-1 degrees of freedom (n equals the number of subjects) to assess the equivalence of these 2 regimens. Equivalence will be demonstrated and the null hypothesis rejected if the limits of the 90% CI fall wholly within the interval of (-4, 4) bleeds per year. See Summary of Changes to Planned Analyses for the Final CSR (Item 4) for further discussion.

Additionally, an ANOVA model appropriate for the crossover design will be employed to test for the presence of treatment sequence, period and carryover effects. The ANOVA model will be fitted with terms for treatment sequence (AB or BA), treatment frequency (A or B), period (study segment 1 or 2), carryover and subject nested in treatment sequence. If one or more of the terms for treatment sequence, period or carryover are statistically significant then exploratory analyses may be prepared to help understand the nature of the effect. See Summary of Changes to Planned Analyses for the Final CSR (Item 6) for further discussion.

ABR will also be presented as descriptive statistics (n, mean, SD, median, interquartile range, minimum, and maximum). ABRs will be summarized by bleed type (ie, spontaneous or traumatic), by bleed location (eg, joint, soft tissue/muscle), and by treatment frequency (ie, prophylaxis A, prophylaxis B).

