3.3.3.7. Compliance to Prophylaxis Regimen

Descriptive statistics will be provided to summarize subject compliance to their assigned prophylaxis regimen (dose [IU/kg] and dose frequency [number of infusions per week]). The number of infusions and the number of days (and weeks) on each assigned prophylaxis regimen will be presented for each subject.

As an exploratory analysis to determine the effect of non-compliance to regimen on ABR, the ANOVA model for the crossover design, described in SAP Section 3.3.2.2, will be fitted with an additional factor for actual treatment frequency (as opposed to prescribed frequency). Actual treatment frequency will be calculated from the number of infusions divided by the number of weeks on treatment, including non-routine prophylaxis infusions.

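### The exploratory compliance model predicts bleed rate from an infusion count that does not exclude infusions given for bleeds, so it can show false frequency and regimen effects

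*SAP*

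**What the plan says.** SAP 3.3.3.7 introduces the model with "As an exploratory analysis to determine the effect of non-compliance to regimen on ABR". The crossover model of SAP 3.3.2.2 "will be fitted with an additional factor for actual treatment frequency (as opposed to prescribed frequency". The predictor is then defined: "Actual treatment frequency will be calculated from the number of infusions divided by the number of weeks on treatment, including non-routine prophylaxis infusions".

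On the outcome, SAP 3.3.2.1 says: "The number of bleeds for the ABR calculation includes all bleeds requiring treatment with a FVIII replacement product during the time on treatment".

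The base model in SAP 3.3.2.2 has "terms for treatment sequence (AB or BA), treatment frequency (A or B), period (study segment 1 or 2), carryover" and subject within sequence. Item 6 of the SAP's Summary of Changes finds this overparameterized and substitutes a "mixed-effect model ABR=sequence period treatment, with subject as a random effect will be used to evaluate the treatment effect". Item 6 does not mention the frequency predictor, so its definition stands.

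On data collection, Protocol 15.1.6 says: "Subjects will document all of their infusions (dose, time of infusion, and reason"). SAP 3.3.3.6 already summarizes consumption by reason for dosing, on-demand or prophylaxis.

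**The concern.** A predictor meant to measure adherence should not move because the subject bled. Here it can. Every bleed counted in ABR was treated with FVIII, so it brings at least one infusion. If that infusion enters the frequency, a subject who bleeds more in one segment has both a higher ABR and a higher actual frequency in that segment, whatever his adherence.

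Two results follow. The frequency slope is pushed upwards, as if more frequent dosing went with more bleeding. And because frequency is added to a model that keeps the regimen term, while the regimens differ in assigned frequency, the false slope also pulls the regimen coefficient away from zero.

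At stake is the only planned model that estimates the effect of non-compliance on ABR. Run as written, it could report a large regimen difference beside an equivalence analysis that shows none.

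**Working it through.** **1. The plan's own figure.** The SAP gives no expected result for this model, but the check uses the inputs of the sample-size re-estimation (SAP 1.4.2), so those were reproduced first. The SD of the within-subject difference is 6.5, the assumed difference 1.3, the margin 4, with a 90% two-sided interval and 80% power. The normal formula gives (6.5 × (1.645 + 0.842) / (4 - 1.3))² = 35.8, so 36. With the t distribution, power is 0.797 at n = 37 and 0.807 at n = 38, so the stated 38 is confirmed. Dropout of 30% gives 38 / 0.70 = 54.3, so 55; the plan states about 56.

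**2. Inputs to the check.**
- From the documents: n = 38; within-subject variance per segment s² = 6.5² / 2 = 21.125; intraclass correlation 0.30. Regimen A is 2 infusions/week ("A: 45 ± 5 IU/kg, administered twice a week"). Regimen B, every other day, is 7 / 2 = 3.5, a gap of 1.5. Mean ABR was set at 6, between the 5.7 and 7.1 quoted in SAP 1.4.2.
- Assumed, not in the documents: k, infusions per bleed, 1 to 2; τ, the SD of routine-dose adherence, 0.1 to 0.5 infusions/week, independent of bleeding.
- True regimen effect and true frequency effect are both zero.

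**3. Closed form, all infusions counted.** One extra bleed per year adds a = k / 52.18 infusions/week. Within subject,

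false slope = a·s² / (a²·s² + τ²), and false B - A coefficient = -1.5 × slope.

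For k = 1.5 and τ = 0.2: a = 0.02875, a·s² = 0.607, a²·s² = 0.0175. The slope is 0.607 / (0.0175 + 0.04) = 10.6 and the B - A coefficient is -15.9.

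**4. Simulation.** AB/BA crossover, 38 subjects, overdispersed Poisson bleeds, 2000 runs per setting. ABR was regressed on subject (as a fixed block), period, regimen and actual frequency. Ranges are over k = 1 to 2.

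| τ (infusions/week) | False slope (bleeds/year per weekly infusion) | False B - A (bleeds/year) | p < 0.05 for regimen |
|---|---|---|---|
| 0.1 | 19 to 22 | -29 to -33 | 99% to 100% |
| 0.2 | 8.2 to 11.2 | -12.3 to -16.8 | 66% to 99% |
| 0.3 | 4.0 to 6.6 | -6.0 to -9.9 | 35% to 86% |
| 0.5 | 1.6 to 2.9 | -2.4 to -4.3 | 16% to 46% |

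At τ = 0.2 and k = 1.5 the simulated means are +10.3 and -15.5, in line with step 3. The closer adherence is to perfect, the larger the artefact, because less genuine variation in frequency is left to dilute it.

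**5. Routine prophylaxis infusions only.** Mean slope is -0.05 to 0.15, mean B - A is -0.23 to 0.11, and rejection is 4.7% to 5.6% at a nominal 5%. Both false effects disappear.

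**6. Narrow reading.** Suppose only off-schedule preventive doses are meant, so on-demand doses drop out. Escalation is triggered by spontaneous bleeds (Protocol 15.3.3) and moves a regimen A subject from 2 to 3.5 infusions/week. SAP 3.3.3 uses the ITT and efficacy-evaluable populations, and neither definition cuts data at escalation. Under an assumed escalation rate (the documents give none), the slope is about +1.8 and B - A about -2.5 at τ = 0.2 (about 14% rejection). At τ = 0.5 they are +0.6 and -0.7 (about 8%).

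**7. Where the regimen coefficient comes from.** Replacing frequency by its deviation from the assigned value leaves the slope unchanged and changes the regimen coefficient to (B - A) + 1.5 × slope. At τ = 0.2 and k = 1.5 that is -15.52 + 1.5 × 10.34 = -0.01. The false regimen coefficient therefore needs both the bleed-driven slope and the 2 versus 3.5 coding. Recoding alone removes the regimen artefact but not the false slope.

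**The case against.** **The model is exploratory.** This stands. Equivalence is judged on the t-based 90% interval of SAP 3.3.2.2, with the margin of Summary of Changes item 4, and neither uses this predictor. SAP 3.3.3 also disclaims hypothesis tests for its endpoints, compliance among them. The rejection rates above therefore show how strong the artefact is; they are not error rates of a planned decision.

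**Non-compliance is handled elsewhere too.** This also stands. The supportive equivalence analysis uses a per-protocol population (SAP 3.2.2.2 and 3.3) that excludes major violators, and SAP 3.7.1 counts routine noncompliance as a major violation. Protocol 16.8 asks the final report to document the impact of extensive noncompliance. A reader might infer that the compliance model is the trial's only safeguard here; it is not. It is only the one planned model that estimates the effect on ABR.

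**The wording may mean off-schedule preventive doses.** That reading is possible, and the split by reason in SAP 3.3.3.6 lends it some support. It reduces the bias but does not remove it (step 6), and the SAP does not say which reading applies.

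**The size depends on assumptions.** True: the false regimen coefficient varies more than tenfold with τ and k. The sign did not change in any setting. The simulation treats subject as a fixed block, whereas item 6 makes it random. Differences between subjects in bleeding also feed both outcome and predictor, so the random-subject model does not remove the problem, though the size may differ.

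**Conclusion.** The definition is wrong as written for its stated purpose: it lets the outcome into the predictor. If all infusions count, the false slope is about +1.6 to +22 bleeds/year per weekly infusion and the false B - A coefficient about -2.4 to -33 bleeds/year. These figures assume 1 to 2 infusions per bleed, an adherence SD of 0.1 to 0.5 infusions/week, and that the regimen term stays in the model, as an additional factor implies. On the narrow reading they are about +0.6 to +1.8 and -0.7 to -2.5, under an assumed escalation rate.

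A reader might infer that the equivalence conclusion is compromised, or that one large figure near the top of the range is what the trial will show. The documents support neither. The primary on-demand comparison and the equivalence interval do not involve this model, and the quantities that set the size are not given. The point is worth fixing because the model cannot answer its own question and the correction is cheap.

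**What to change.** Amend SAP 3.3.3.7 as follows:
- Define actual frequency as infusions recorded as routine prophylaxis on the assigned regimen, divided by weeks on that regimen. Exclude bleed-treatment, follow-up and surgical infusions.
- For this model, censor infusions, weeks and bleeds at regimen escalation. The recorded reason alone is not enough, because doses after a bleed-triggered escalation would still be recorded as routine prophylaxis.
- Enter frequency as the deviation from the assigned frequency (2 or 3.5 per week) in the mixed model of Summary of Changes item 6, so that it is not nearly collinear with regimen.

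The cost is SAP wording and programming; the diary data needed are already collected. The downside is that data after escalation are not used in this exploratory model.

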3.4. Safety Endpoints

Safety data will be collected during the entire course of the study starting from the time informed consent is signed. All safety data collected after informed consent/assent is obtained will be displayed in a listing format. All safety analyses will be performed on the ITT analysis population, additionally adverse events, lab data, and the incidence of inhibitor development will be performed on the mITT population.

3.4.1. Adverse Events and Allergic Reactions

3.4.1.1. Variable Definitions

Safety endpoints are adverse events (AEs) and include AEs that are allergic reactions.

Adverse events (including allergic reactions) with onset or worsening after the first dose of moroctocog alfa (AF-CC) administration are considered treatment emergent adverse events (TEAEs). This study does not collect onset time of AEs. Therefore an AE with a start date on the same day of the study drug administration will be counted as a TEAE unless there is further information to support that the AE occurred prior to the study drug administration.

3.4.1.2. Analysis Methods

The number (%) of subjects who experienced TEAEs will be reviewed and summarized by relatedness to the study drug and by maximum severity grade. Descriptive statistics (number and frequency) will be provided for all adverse event summaries. No hypothesis testing will be carried out.

3.4.2. Other Safety Endpoints

For change from baseline calculations, the closest non-missing value collected before the first dose of moroctocog alfa (AF-CC) will be considered baseline.

Normal ranges of the laboratory tests provided by the central lab and local labs will be used to flag abnormal test results.

Patient serum samples will be collected and tested for the development of antibodies both neutralizing and nonneutralizing) to moroctocog alfa (AF-CC), using a validated ELISA.

3.4.2.1. Inhibitor Development

Incidence of FVIII inhibitors to moroctocog alfa (AF-CC) will be monitored throughout the duration of this study. A subject will be considered to have developed a confirmed positive inhibitor if he has a titer of ≥ 0.6 Bethesda Units (BU)/mL in a sample assayed at the central laboratory using the Nijmegen assay. The occurrence of an inhibitor will be reported as an SAE. This determination will be based on the mITT population. See Summary of Changes to Planned Analyses for the Final CSR (Item 5) for further discussion.

3.4.2.2. Laboratory Test Results

Abnormal lab test results will be presented. The significance of the mean change from baseline for all subjects for each of the serum chemistry and hematology assays will be assessed clinically and the 95% confidence interval of the mean change at each visit will be presented. Out-of-range results will be listed separately.

3.4.2.3. Concomitant Medications

Any use of concomitant medications will be listed by subject. Bleeding episodes treated with replacement products other than test article will be listed separately from bleeds treated with test article as well as in the concomitant medication listing.

3.4.2.4. Vital Signs

Vital signs and physical examinations will be listed for each visit. Changes from baseline to any subsequent visit will be assessed clinically.

3.5. Missing Data

Missing data will be reported as such and no imputation will be made unless otherwise specified. The proportion of data that is missing for key variables will be presented if appropriate. The study will diligently collect all the data as planned. If any pattern of missing data is identified, extra effort will be made to ensure that the analysis is not affected by the circumstances.

3.6. Analysis Data Sets

There will be analysis data sets created for use in the analysis.

3.7. Description of Study Deviations

3.7.1. Major Protocol Violations

The following are the criteria for the major protocol violations:

- Inclusion or exclusion criteria not met and not exempted;
- Frequent (per clinical judgment) use of nonstudy FVIII concentrates during the study;
- Routine, concomitant treatment with prohibited immunomodulating drugs;
- The use of other investigational agents during the study;

- Frequent (per clinical judgment) use of drugs with antiplatelet activity (eg., aspirin);
- Routinely noncompliant with protocol-specified procedures.

Subjects with major protocol violations should be removed from study per the medical monitor's discretion. Protocol violations or deviations will be listed in the study report.

3.8. Multicenter Handling

Because relatively small numbers of subjects will be enrolled at each site, no test of homogeneity across sites will be performed. Data will be pooled from all sites for analysis.

3.9. Subgroup Analysis

No subgroup analyses are planned other than those described in Section 2.3 and Section 3.2.

3.10. Statistical Software

SAS v9.1.3 (or current version) will be used to perform all efficacy and safety analyses.

REFERENCES

1. J. Ogawa (1983): On the confidence bounds of the ratio of the means of a bivariate normal distribution. Ann. Inst. Statist. Math., 35, 41-48.

APPENDIX A: SUBJECT NARRATIVES

Subject narratives will be available for the categories established according the International Conference on Harmonisation (ICH) guidelines. A narrative will be provided for subjects who met 1 or more of the following criteria:

- Serious adverse events;
- Death;
- Inhibitor development;
- Less-than expected therapeutic effect;
- Discontinuation due to an adverse event.

